## **List of Abbreviations**

SEMS; Self Expanding Metal Stents

ERCP; Endoscopic Retrograde Cholangiopancreatogram

CBC; Complete Blood Count

CMP; Comprehensive Metabolic Panel

INR; International Normalized Ratio

1 Study Summary

Title	Preoperative Endoscopic Biliary Drainage with Self Expanding Metal Stents (SEMS) vs. Direct Surgical Resection for Patients with Severe Obstructive Jaundice
Short Title	Pre-surgery biliary stent placement vs. direct surgery in patient with obstructive jaundice
Protocol Number	
Phase	N/A
Methodology/Study Design	Randomized control trial
Study Duration	24 months
Study Center(s)	Thomas Jefferson University
Objectives	Investigate the advantage of using biliary SEMS in patients with severe jaundice prior to surgical resection
Number of Subjects	100
Diagnosis and Main Inclusion Criteria	Patients with periampullary cancer with profound jaundice
Study Therapy, Dose, Route, Regimen	Pre-operative SEMS placement vs direct surgical resection
Duration of administration and follow-up	Patient outcome data will be monitored at 30 days and 90 days post resection surgery.
Reference therapy	Direct surgery without stent placement
Statistical Methodology	This is a superiority trial of early surgery without biliary stenting, as compared with preoperative biliary drainage in patients with severe obstructive jaundice
Schema	<pre> graph LR     A[100 patients] --> B[50 patients with preoperative stent placement]     A --> C[50 patients without preoperative stent placement]     B --> D[Grade III or higher complication]     B --> E[No complications]     C --> F[Grade III or higher complication]     C --> G[No complications]   </pre>

3        **1.0 INTRODUCTION**

4        Pancreatic cancer is the second most common digestive cancer and fourth leading cause of cancer  
5        death in the United States for both men and women. Pancreatic tumors arising in the peri-  
6        ampullary region present with biliary obstruction in 64-77% of cases. Preoperative biliary  
7        decompression has been advocated in an attempt to reduce postoperative complications following  
8        attempted curative-intent surgery.

9  
10      This document is a protocol for a human research study. This study is to be conducted according  
11      to US and international standards of Good Clinical Practice (FDA Title 21 part 312 and  
12      International Conference on Harmonization guidelines), applicable government regulations and  

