13      Institutional research policies and procedures.

14        **1.1 Specific Aims and Hypothesis**

15        The primary aim of this study is to compare the 30 and 90-day overall/cumulative grade III or  
16        higher complication rates between patients with severe obstructive jaundice undergoing  
17        preoperative endoscopic biliary drainage with SEMS and patients undergoing direct surgical  
18        resection. In this study, **One arm undergoes preoperative biliary drainage followed by surgery and**  
19        **the other arm undergoes surgical resection** without prior biliary drainage. Secondary aims will be  
20        to compare surgical outcomes including mortality, intra-operative parameters, hospital length of  
21        stay, ICU length of stay, readmission rate and time to commencement of adjuvant treatment.

22        **1.2 Background and Rationale**

23        Despite the fact that endoscopic and percutaneous placement of biliary stents is technically  
24        successful in 90-95% of cases, routine preoperative biliary drainage for pancreatic cancer remains  
25        controversial.[4, 5] Pooled data from retrospective studies published over the past several years  
26        have shown similar rates of 30-day mortality after pancreaticoduodenectomy in those who have  
27        undergone biliary decompression as compared to those who have not. A few studies have  
28        suggested that routine preoperative drainage in patients undergoing surgery for cancer of the  
29        pancreatic head may increase overall complications, likely due to complication related to the  
30        endoscopy itself (i.e. pancreatitis, bleeding, perforation) and complications related to stent  
31        failure.[6] In the largest, multicenter, randomized trial to date, patients were randomly assigned  
32        to undergo either endoscopic preoperative biliary drainage for 4 to 6 weeks, followed by surgery,  
33        or surgery alone after diagnosis. In this study, endoscopic preoperative biliary drainage did not  
34        have a beneficial effect on the surgical outcome but rather was associated with an increase in  
35        serious complications.[7]

36  
37        On the other hand, outcome measures have not been standardized and the lack of complete data  
38        on surgical complications following preoperative drainage make direct comparisons difficult and  

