65 obstruction prior to surgery. This represents the first biliary metal stent with labeling to support  
66 pre-operative drainage in the US.

67 **1.4 Preclinical Data**

68 Please see clinical data below

69 **1.5 Clinical Data to Date**

70 A recent meta-analysis of 1989 patients showed that SEMS have higher stent insertion success,  
71 lower risk of stent occlusion, lower re-intervention rate, fewer therapeutic failures, and fewer  
72 episodes of cholangitis compared to plastic stents making them the optimal choice for biliary  
73 decompression.[8] Also a recent randomized controlled trial confirmed that SEMS are superior to  
74 plastic stents with regard to functional stent time and showed that the total health care cost is  
75 similar for placing SEMS or plastic stents even in patients with survival less than 3 months

76 **1.6 Dose Rationale and Risk/Benefits**

77 The study doesn't involve drug administration.

78 **2.0 STUDY OBJECTIVES**

79 **2.1 Primary Objective:**

80 The primary aim of this study is to compare the 30 and 90-day overall complication rates between  
81 patients with severe obstructive jaundice undergoing preoperative endoscopic biliary drainage  
82 with SEMS and patients undergoing direct surgical resection.

83 **2.2 Secondary Objective:**

84 Secondary aims will be to compare surgical outcomes including hospital length of stay, ICU  
85 length of stay, readmission rate, disposition from hospital, emergency room visits, urgent care  
86 center visits and time to commencement of adjuvant treatment.

87 **3.0 STUDY DESIGN**

88 **3.1 General Design**

89 This is a Randomized controlled trial.

92 ERCP will be performed on those who are randomized to the intervention group with 24 hours of  
93 randomization. The patient will be followed at 30 days and 90 days post-operatively.

94 **3.2 Primary Study Endpoints**

95 30 and 90 day- complication rates between patients with severe obstructive jaundice undergoing  
96 preoperative endoscopic biliary drainage with SEMS and patients undergoing direct surgical  
97 resection

98 **3.3 Secondary Study Endpoints**

99 Secondary aims include the total number of complications, intraoperative estimated blood loss,  
100 number of required fluid boluses, postoperative hospital LOS, readmission rate, disposition from  
101 hospital, time to commencement of adjuvant treatment, emergency room visits, urgent care center  

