102 visits, and perioperative mortality. Complications will include pancreatic fistula, delayed gastric  
103 emptying, intra-abdominal abscess, cardiac complications, respiratory complications, deep vein  
104 thrombosis, pulmonary embolism, urinary tract infection, wound infection, acute renal failure,  
105 hemorrhage, hepaticojjunostomy leak, and duodenojjunostomy leak. Pancreatic fistula was  
106 defined and graded according to the International Study Group of Pancreatic Fistula criteria.  
107 Delayed gastric emptying was defined and graded according to the International Study Group of  
108 Pancreatic Surgery. Wound infections and urinary tract infection were defined according to the  
109 Centers for Disease Control and Prevention guidelines. Cardiac complications were defined  
110 according to the American College of Cardiology and renal complications were defined by the  
111 Acute Dialysis Quality Initiative.

112 **3.4 Primary Safety Endpoints**

113 Both SEMS placement and direct surgical resection are considered acceptable standard of care  
114 practices.

115 **4.0 SUBJECT SELECTION AND WITHDRAWAL**

116 **4.1 Inclusion Criteria**

117 -Adult patients age >18 regardless of gender or ethnicity  
118 -Patients with peri-ampullary pancreatic cancer.  
119 -Patients with serum bilirubin greater than 10mg/dL  
120 -Adequate birth control

121 **4.2 Exclusion Criteria**

122 -Patients with evidence of distant metastasis on CT or MRI  
123 -Patients anticipated to require vascular reconstruction  
124 -Patients with cholangitis  
125 -Patients who previously underwent biliary decompression for cholangitis by ERCP or PTC  
126 -Patients with low performance score (Karnofsky performance status scale < 50)  
127 -Patients with known preexisting liver disease with associated elevated bilirubin  
128 -Patients who are pregnant or actively breast feeding.

129 **4.3 Gender/Minority/Pediatric Inclusion for Research**

130 Any patient can be included if older than 18 years of age irrespective of gender, color, or  
131 ethnicity.

133 4.4 Subject Recruitment and Screening

134 One Hundred patients older than 18 years with periampullary cancer presenting with jaundice and  
135 total bilirubin greater than 10mg/dL will be included in the study.

136 Patients will be recruited from clinic (gastroenterology and pancreaticobiliary surgery) or when  
137 admitted to the hospital for workup and/or management and will be consented at that time.

138

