170 The stent will placed by ERCP and won't be removed before surgery unless indicated. Follow up  
171 phone calls to ascertain secondary endpoints will be made at 30 and 90 days.

172 5.7 Prior and Concomitant Therapy  
173 Subject in the study are to continue any medications that they are on. Those who are randomized  
174 to the intervention group may be asked to hold antiplatelet/anticoagulation agents prior to the  
175 ERCP in coordination with their prescribing doctor.

176 5.8 Blinding of Study Drug  
177 Unblinded study

178 **6.0 STUDY PROCEDURES**

179

180 **6.1 Study Visit Schedule**

181 **Screening:**  
182 Patients will be screened in clinic or if admitted as inpatients. Patient must satisfy the inclusion  
183 criteria listed above. Patient must carry a diagnosis of per-ampullary cancer. Basic labs will be  
184 withdrawn including CBC, CMP and INR.

185

186 **Randomization**  
187 **Peri-operative:** The patient will be admitted and labs will obtained including CBC, CMP and  
188 INR prior to surgery.

189

190 **Post-operative:**  
191 Visit 1: This will be scheduled 3-4 weeks after hospital discharge. Labs and imaging may be  
192 ordered by the surgeon if needed.

193 Follow-up  
194 Patients will be followed up to 90 days after the surgery. A phone call will be placed to the  
195 patient by research staff to ascertain secondary endpoints. Jefferson EMR will be accessed  
196 to ascertain primary endpoint data.

197

198 **7.0 STATISTICAL PLAN**

199 7.1 Sample Size Determination  
200 Based on previous data, we assumed an overall grade III or higher complication rate of  
201 50% in the control group. Although we are unsure of the expected rate in the pre-operative  
202 biliary stenting group, a 30% or greater reduction in the grade III or higher complication

would be meaningful. The sample size will be 100 subjects (50 per arm). We calculated power under various alternatives for the biliary stenting group complication rate using a two-group large-sample normal approximation test of proportions, with a one-sided significance level of 0.05, to test the null hypothesis that the grade III or higher complication rate in surgery with biliary stenting is greater than or equal to the control rate (50%). We have 84% power to detect a reduction if the true rate with biliary stenting is 25%, 66% power if the true rate is 30%, and 44% power if the true rate is 35%.

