## 7.2 Statistical Methods

Baseline characteristics will be summarized by randomization arm using means, standard deviations, and ranges for continuous variables and counts and frequencies for categorical variables.

Rates of grade III or higher complication rates will be estimated separately at 30 and 90 days. The risk difference will be calculated (stent minus control) with a one-sided 95% confidence interval. If the upper bound of the confidence interval is less than 0 at both times, surgery with biliary stenting will be considered effective at reducing the rate of grade III or higher complications.

Group comparisons with respect to continuous outcomes will be performed using two-sample t-tests or Wilcoxon rank sum tests. Comparisons for categorical outcomes will be performed using chi-square tests or Fisher's exact test. Comparisons for count outcomes will use Poisson regression. Kaplan-Meier analysis will be used to estimate the distribution of time-to-event outcomes. Groups will be compared using the log rank test.

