## 7.3 Subject Population(s) for Analysis

All randomized patients will be included in the analysis as randomized. A per-protocol analysis will be performed if there are any patients who do not receive the assigned surgical technique.

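### Time to adjuvant treatment has no defined time origin and no rule for deaths, and a plain Kaplan-Meier estimate would overstate the proportion starting

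*Combined protocol and SAP*

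**What the plan says.** Section 7.2 of the combined protocol and SAP has two sentences on time-to-event outcomes: "Kaplan-Meier analysis will be used to estimate the distribution of time-to-event outcomes", and "Groups will be compared using the log rank test". It names no outcome, time origin, censoring rule or competing-risk method.

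Sections 1.1, 2.2 and 3.3 list "time to commencement of adjuvant treatment" among the secondary outcomes. No other listed outcome is worded as a time to an event. Section 3.3 ends its list with "visits, and perioperative mortality", so the plan expects some deaths.

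Outcome follow-up is tied to the operation. The Study Summary says "Patient outcome data will be monitored at 30 days and 90 days post resection surgery", section 3.1 repeats the 30- and 90-day schedule, and section 6.1 says "Patients will be followed up to 90 days after the surgery". Section 5.6 adds phone calls at 30 and 90 days for the secondary endpoints. Only the adverse-event reporting period, in section 8.1, is stated to begin at randomisation.

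Section 7.3 says "All randomized patients will be included in the analysis as randomized".

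**The concern.** Two gaps meet in this endpoint.

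First, a patient who dies before adjuvant treatment can never start it. A standard Kaplan-Meier run has only two states, event and censored. A death entered as censored is treated as a patient who might still start later. The complement of the curve (1-KM), read as the proportion who started, is then too high, and more so in the arm with more deaths.

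Second, the arms differ by design in how long patients wait for surgery, because one arm is drained first. Later adjuvant treatment is one of the possible costs of drainage that this endpoint could show. If time is counted from surgery, the difference in wait is removed before the arms are compared. Patients who are randomised but never resected would have no starting point at all.

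The study is unblinded (section 5.8), so an origin left open can be chosen after the data have been seen.

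**Working it through.** **Plan's own figures.** The plan gives none for this endpoint. Its only design figures are the section 7.1 powers for the primary endpoint (84%, 66%, 44%). A one-sided 0.05 test of two proportions with 50 per arm and pooled null variance gives 83.4%, 65.7% and 44.9%. They reproduce within a point and do not bear on this issue.

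**Step 1: deaths censored.** Let F be the true proportion starting by day 90 and D the proportion dying first. The documents give neither; F = 60% and D = 3%, 5% and 10% are assumptions. Three models:

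- Constant hazards: 1-KM = 1 - (1 - F - D)^(F/(F+D)). For D = 5%: 1 - 0.35^(0.60/0.65) = 1 - 0.379 = 62.1%.
- Delayed start: daily hazards, no starts until after day 28, and a death hazard that falls to 30% of its initial value after day 45; solved numerically to give the same F and D.
- Limiting case, all deaths before the first start: 1-KM = F/(1 - D). For D = 5%: 0.60/0.95 = 63.2%.

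| Deaths by day 90 | True proportion starting | Constant hazards | Delayed start | Limiting case |
|---|---|---|---|---|
| 3% | 60% | 61.2% | 61.7% | 61.9% |
| 5% | 60% | 62.1% | 62.8% | 63.2% |
| 10% | 60% | 64.4% | 66.0% | 66.7% |

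The excess under the first two models is 1.2 to 2.8 points at 3-5% deaths and 4.4 to 6.0 points at 10%; the limiting case adds at most 0.7 of a point. With F between 50% and 70% and D between 3% and 10%, the delayed-start model gives 1.4 to 7.2 points.

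**Step 2: the clock.** For a resected patient, time from randomisation is the wait for surgery plus time from surgery. So, on average,

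(stent - control, from randomisation) = (stent - control, from surgery) + (stent wait - control wait).

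A surgery clock omits the last bracket. Section 3.1 puts ERCP within a day of randomisation, but no interval to surgery is given for either arm. As an illustration only, take 28 to 42 days for the stent arm, which is the 4 to 6 weeks that section 1.2 reports for an earlier trial, and assume a control wait:

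| Assumed control wait | Days omitted from the comparison |
|---|---|
| 0 days | 28 to 42 |
| 7 days | 21 to 35 |
| 14 days | 14 to 28 |

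**Step 3: effect on the test.** The simulation used 50 per arm, 1,500 runs and a two-sided 0.05 log-rank test. Both arms had the same surgery-to-adjuvant distribution: Weibull with shape 3, median 56 days among eventual starters, and 25% never starting. Control patients waited 7 days; all waits varied by up to 3 days either way. Follow-up ended 90 days after surgery, and deaths were not simulated. All these inputs are assumptions.

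| Stent wait | Rejects, clock from surgery | Rejects, clock from randomisation |
|---|---|---|
| 14 days | 5.9% | 12.3% |
| 21 days | 4.3% | 34.3% |
| 28 days | 5.1% | 68.3% |
| 35 days | 4.4% | 92.5% |
| 42 days | 4.8% | 98.7% |

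From surgery, the test rejects at about its nominal rate however long the extra wait is. From randomisation, the chance of detecting the delay rises with the wait.

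**Step 4: population.** Section 7.3 keeps every randomised patient. A surgery origin is undefined for a patient who is never resected, so the two cannot both hold for this endpoint. A randomisation origin is defined for everyone.

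**The case against.** The strongest reply is that the plan is brief here rather than wrong, and much of that stands. A reader might infer several stronger points that the documents do not support.

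- *That the plan censors deaths.* It states no censoring rule. Censoring is what a standard Kaplan-Meier run does with a death before the event; it is not a written choice.
- *That section 7.2 names this endpoint.* It does not. Kaplan-Meier could also be meant for perioperative mortality, where death is the event and no competing risk arises. Adjuvant start is the likeliest target because of its wording.
- *That all follow-up runs from surgery.* Section 8.1 starts the adverse-event period at randomisation. The other sections fix assessment times and the end of follow-up, not time zero for this endpoint. The conflict with section 7.3 therefore arises only if a surgery origin is chosen.
- *That the log-rank test is invalid.* With deaths censored it is a valid test of the cause-specific hazard. The bias is in 1-KM read as a proportion, and the plan does not say that it will report that proportion.
- *That a stent arm 10 days faster after surgery would really be 18 to 32 days slower.* That is 28 - 10 and 42 - 10, and it assumes that control patients wait no time at all for surgery. With a 7-day control wait it is 11 to 25 days, and with 14 days 4 to 18. None of these waits is given for this trial.

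The censoring bias is also modest beside sampling error. With 50 per arm, the standard error of a 60% proportion is √(0.6 × 0.4/50) = 6.9 points, and of a between-arm difference 6.9 × √2 = 9.8 points. If 3% die in one arm and 5% in the other, the between-arm distortion is about 1 point (62.1 - 61.2 = 0.9).

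What the reply does not remove is the undefined origin, or the fact that the one method stated has no place for death as a competing event.

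**Conclusion.** The point holds as an under-specified secondary analysis with a better method readily available. Under the stated method, the proportion starting adjuvant treatment would be overstated by about 1 to 3 points at an assumed 3-5% mortality and 4 to 6 points at 10%, if 60% truly start. The open time origin is the more consequential gap. If it is set at surgery, the comparison loses the drainage interval minus the control arm's wait, and unresected patients fall out despite section 7.3. The size of that loss for this trial cannot be stated, because neither interval is given; the day counts and rejection rates above are illustrations. The documents do not show that the sponsor has chosen to censor deaths or to start the clock at surgery. Only a secondary endpoint is affected, so the priority is low.

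**What to change.** In section 7.2:

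1. Define the endpoint as time from randomisation to the first adjuvant treatment, in all randomised patients.
2. Replace 1-KM with the cumulative incidence of starting (Aalen-Johansen estimator), with death before start as a competing event.
3. Keep unresected patients and other non-starters in the risk set as not started, up to a stated common horizon from randomisation.
4. Name one comparison in advance: Gray's test, or the cause-specific log-rank test. The second is the ordinary log-rank with deaths censored, so the test already named can stay.
5. Report time from surgery as descriptive only.

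The cost is a few sentences and a standard software routine, with three cautions. Time from randomisation is less familiar to surgical readers. The common horizon involves a trade-off, because follow-up ends 90 days after surgery: a 90-day horizon from randomisation is covered for every resected patient but, with an assumed 28- to 42-day drainage interval, shows only 62 to 48 days after surgery in the stent arm (90 - 28 and 90 - 42), while a longer horizon may need extra control-arm follow-up. Finally, the case report form is not shown, so it must be confirmed that it records the adjuvant start date and an end of follow-up for unresected patients; section 5.6 describes only phone calls at 30 and 90 days.

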## 7.3 Subject Population(s) for Analysis

All randomized patients will be included in the analysis as randomized. A per-protocol analysis will be performed if there are any patients who do not receive the assigned surgical technique.

## 8.0 SAFETY AND ADVERSE EVENTS

### 8.1 Definitions

#### Adverse Event

An **adverse event** (AE) is any symptom, sign, illness or experience that develops or worsens in severity during the course of the study. Intercurrent illnesses or injuries should be regarded as adverse events. Abnormal results of diagnostic procedures are considered to be adverse events if the abnormality:

- results in study withdrawal
- is associated with a serious adverse event
- is associated with clinical signs or symptoms
- leads to additional treatment or to further diagnostic tests
- is considered by the investigator to be of clinical significance

